EEG Cap for Identification of Non-Convulsive Status Epilepticus

NCT# 03138876

February 22, 2017

RESEARCH PROTOCOL OUTLINE

Title: EEG Cap Placement for Expedited Identification of Non-Convulsive Status Epilepticus

Principal Investigator: [name] D.O.

Co-Investigators: [name] M.D., [name] M.D., [name] D.O., [name] M.D., [name] M.D., [name] D.O., [name]

Abstract

Altered mental status (AMS) is one of the most common reasons for inpatient neurology consultation. Non-convulsive status epilepticus (NCSE) is frequently a differential diagnosis of the patient with AMS. NCSE becomes more refractory to treatment after one hour of seizure activity, making rapid identification and treatment of NCSE of great clinical importance. Currently, an EEG technician must be called in from home during non-workday hours in order to obtain a stat EEG. We propose the time required for diagnosis of NCSE in our institution can be significantly decreased with rapid placement of an EEG cap by the onsite neurology residents.

A. Specific Aims

1. Utilize EEG cap for rapid assessment of seizure activity in 20 patients with suspected NCSE
2. Rapid EEG review by on-call resident & attending physicians
3. Employ existing standard of care for NCSE evaluation with standard electrodes as soon as technician can apply them (cap to not delay standard of care)
4. Evaluate endpoints for cap vs. standard electrodes of time from consultation to:
 - a. completed EEG
 - b. Diagnosis or exclusion of NCSE

B. Background and Significance

Status epilepticus is operationally defined as a seizure greater than five minutes in duration or more than one seizure within a five minute period without return to normal baseline mental status. Convulsive status epilepticus is a medical emergency. Status epilepticus is more likely to become refractory to medical therapy when treatment is delayed for over 1 hour (DeLorenzo et al). NCSE is a persistent change in behavior and processes from baseline associated with continuous epileptiform EEG changes, but without major motor signs. Nonconvulsive status epilepticus (NCSE) in a comatose patient cannot be diagnosed without electroencephalography (EEG). A previous study has demonstrated the urgency of rapid identification and treatment of NCSE (Meierkord et al). Hospital neurology programs frequently rely on EEG technologists who are on-call but not onsite to place EEG electrodes that are used for assessment of NCSE. EEG caps allow for more rapid electrode placement and EEG analysis, but there exists ambiguity whether rapidly placed caps are sufficiently accurate to reliably identify NCSE for clinical decision-making. Use of EEG cap (also referred to as EEG headsets) in the inpatient setting by onsite neurology providers, if sufficiently reliable versus standard of care electrode-placement, may allow for more rapid identification of NCSE and associated expedited pharmacological treatment.

C. Study Design, Methods, & Statistics

Study will be of prospective design involving 20 patients evaluated at the Mayo Clinic emergency department or hospital that are referred to neurology for evaluation of mental status changes or suspected seizures.

Review type: minimal risk

Is this an interventional study? Yes No

At the completion of neurology evaluation, if NCSE is in the differential diagnosis according to institution best practice, then consented participants will undergo placement of a large size, 20-channel EEG cap from Electro-Cap International with a Natus E-2-2520-26 electrode board adapter with initiation of recording. The placement of the EEG cap will be restricted to residents formally trained in its placement by an EEG tech. The EEG-cap is already owned by the Mayo Clinic Neurology department, and therefore we will not require further funds to obtain equipment for this study. This study will only be performed during times when EEG techs are not available onsite for rapid placement of standard 21-channel EEG electrodes, such as during night-call shifts. We will not bill for the EEG cap placement, only the subsequent standard EEG protocol which will be followed after the EEG-cap placement.

Prior to placement of EEG cap, evaluating staff member will request stat standard-electrode EEG. We will record time from neurology consultation request to placement of EEG cap as well as time from consultation request to obtaining a standard EEG. We will also record time to confirmation or exclusion of NCSE. Initial diagnosis or exclusion of NCSE will be performed by on call resident, if they received prior training regarding EEG cap placement, and attending. Secondary quality assessment will be performed by two independent EEG interpreters blinded to clinical history. Secondary assessment will be qualified as acceptable or unacceptable interpretation based on whether greater or less than 50% of the recording is judged interpretable. Secondary assessment will also include interpretation of NCSE by a third independent reader if there is disagreement between first two. The number of patients excluded from the study will also be recorded, including the reason for exclusion.

Specific data points for statistical analysis include:

- Time of consultation
- Time of standard-electrode EEG order
- Time that 10 minutes of EEG have been completed (for both cap & standard-electrodes)
- Time that 20 minutes of EEG have been completed (for both cap & standard-electrodes)
- Time of diagnosis or exclusion of NCSE

Primary outcome measure: time from stat EEG order to diagnosis or exclusion of NCSE

Secondary outcome measures include:

- Overall quality of cap recordings as operationalized by:
 - Aforementioned >50% interpretability
 - Concordance between cap & standard-electrode diagnostic assessments
- comparison of diagnostic assessments/concordance between 10 and 20 minute captures

Statistical methodology: chi-square and Student T-test will be employed to compare categorical variables.

Data storage and PHI: Initial data collection will be to a password-protected Excel spreadsheet that is only accessible by the study authors. No PHI will be collected, but a unique identifying number will be used to initially distinguish between patients. Data will then be aggregated for statistical analysis. The final paper will only include patient data in aggregate form.

D. Preliminary Studies/Progress Report

EEG is the only definitive way to diagnose NCSE. Although useful, standard surface EEG can be a cumbersome, complex and time-consuming process, all of which can limit its applicability in emergent time-sensitive clinical situations and rural areas without available technology, financial resources or neurophysiologic expertise. EEG headsets, caps or “dry EEG” have been developed and have become commercially available over the past few decades and have been used in multiple brain computer interface (BCI) studies, evoked potentials and biofeedback (Halford, et al, Slater et al). This novel technology does not require measurement of relative electrode differences by EEG technologists or pose increased risk for skin abrasions. Disadvantages EEG caps do exist which may affect its clinical suitability, including movement artifact, sweat artifact and increased weight of the system (Halford, et al).

Some studies have investigated the time differences and validity of EEG headsets versus standard EEG recordings in various clinical scenarios. For instance, a study demonstrated that application of an EEG caps in comparison to a standard EEG was performed over 15 minutes faster, with 87% of the EEG being interpreted as technically adequate. In addition, patients preferred the EEG caps over the standard EEG (Halford, et al). The EEG headset recordings were also felt to be adequate in identifying status epilepticus and were significantly faster to set up (Slater et al). “Light” EEG has also been shown to be comparable to standard EEG in detecting findings suggestive of hepatic encephalopathy, but with higher proportion of light EEG samples being discarded due to artifact (Schiff et al).

Data in identifying epileptiform activity or NCSE utilizing EEG caps is lacking. Disposable forehead electrodes have also been shown to identified status epilepticus, although studies have included a limited number of patients with NCSE and the results have been variable (Myllymaa et al) (Muraja-Murro, et al). In one study, only two out of four patients with status epilepticus were identified with forehead electrodes due to EEG abnormalities being restricted to the posterior regions of the brain (Muraja-Murro, et al).

Due to the small sample sizes, limited number of patients with NCSE and variable electrode placements in prior studies, it remains unclear the applicability of EEG caps in the identification of NCSE, which our study seeks to investigate further. In addition, we plan to readdress the quality and interpretability, as well as the time taken from ordering to interpretation of the EEG cap compared to standard EEG.

E. Gender/Minority/Pediatric Inclusion for Research

Gender and ethnicity will not be used as exclusion criteria when selecting patients. The study will include both men and women. Pediatric patients under the age of 18 will be excluded from our study to permit use of adult size EEG cap for all participants.

F. Human Participants

Inclusion:

1. Patients with suspected NCSE in the Mayo Clinic Florida hospital, emergency room or intensive care unit.
2. Age: Patients of 18 years or older will be included in this study

3. Education: All education levels will be included

Exclusion:

1. Patients younger than 18 years of age.
2. Patients with open head trauma.
3. Patients with anatomy that would preclude EEG cap placement.
4. Patients excluded for anatomical or age-related reasons will be tracked to determine applicability of the EEG cap to the patient population at Mayo Clinic.
5. Pregnant females
6. Large head size not amenable to cap placement
7. Scalp infection
8. Inability to obtain informed consent

Informed Consent:

Patients will lack the capacity to consent, as by definition patients in NCSE have very impaired mental status. NCSE is an emergency, and our protocol is an emergency evaluation. The procedure we are following is minimal risk, and we will still provide the typical standard of care for patients with suspected NCSE. Therefore we will obtain prior verbal consent from a healthcare proxy. If patients regain ability to interact and accurately answer questions while the study is being performed, the study will be stopped, as they would be unlikely to be in NCSE.

Standard of care will be followed in context of emergent intervention. Consent from HCPOA or next of kin or will be obtained, per Florida hierarchy. If the legally authorized representative (LAR) is not available at bedside, an attempt will be made to contact them by way of phone. Given the treatment of NCSE is an emergency, if the first LAR is not available, the Florida hierarchy of consent will be followed with regard to an alternate source of consent.

The use of EEG caps is acceptable for assessment of epilepsy, and, additionally, we will still provide our typical standard of care. The research presents no more than minimal risk of harm to subjects and involves no procedures for which written consent is normally required outside of the research context. Therefore, verbal consent following the Florida Hierarchy of Consent with documentation of the individual consenting in the chart is appropriate.

The consent will be obtained through a discussion with the patient's healthcare proxy at bedside if possible. If no healthcare proxy is available at bedside, a call will be placed to the appropriate healthcare proxy. As the placement of the EEG cap for detection of NCSE is an emergency, the time dedicated to discussion is anticipated to be 2-3 minutes in order to present the risks and benefits of the procedure. The healthcare proxy will be clearly described the risks and benefits of the procedure. They will be offered a waiting period between discussion and decision, and they will be explicitly told that the patient's overall care, outside of the context of the study, will not change based on their decision. Residents responsible for consenting patients in the study will formally complete the consent training in the Mayo Clinic Simulation Center regarding proper technique. Informed verbal consent will be documented on the neurology consult note.

Given the nature of the project aimed at expeditiously identifying NCSE the following details will be verbally provided to health care proxies prior to placement of the EEG cap:

- The study involves assessing patient brain waves with an experimental EEG cap to attempt to diagnose and treat seizures that do not produce convulsive movements, but can alter mental status.

- The cap could identify seizures before the normal method of analyzing brain waves will be performed, which could potentially allow for earlier treatment.
- There is minimal risk, with main risk being that cap may be inaccurate and might be misinterpreted. The risk of misdiagnoses, leading to inappropriate diagnosis and treatment is likely small, but exact data is not available.
- The normal method of analyzing brain waves will be used either way as fast as possible
- Do not feel obligated to consent if you prefer for our typical protocol to be followed. The patient's overall care, outside of the context of this study, will not change based on your decision.
- If you would like some time to think about this decision, I will attempt to return at a time of your choosing.

G. Risks and benefits:

This study is considered minimal risk given the only deviation from standard of care involves application of EEG cap prior to standard of electrodes. To the extent that cap electrodes might be misinterpreted due to theoretically poorer quality risks include:

- Misinterpretation of EEG so as to miss seizure activity, which would not affect time to treatment, given we will still be following and giving priority to our standard protocol.
- Misinterpretation of EEG so as to diagnose non-seizure activity as epileptiform, which is unlikely as attendings will avoid diagnosing NCSE if there is any uncertainty in the EEG.

1. Procedures protecting against or minimizing potential risks:
 - a. Patients will be evaluated by neurology residents or faculty members
 - b. EEG cap will be applied by neurology staff and cleaned between each use
 - c. Electronic data will be stored in a password-protected Excel spreadsheet that contains no PHI
 - d. Regular EEG protocol will be followed in addition to EEG cap placement. Standard electrode placement will be given priority in the event EEG technician is available before EEG cap is placed. There will be no deviation from the current standard of care.
2. Future benefits and importance to the participants and others:
 - a. Use of EEG cap technology can expedite diagnosis of or exclusion of NCSE.
 - b. Rapid identification of NCSE can reduce time to treatment, which may improve patient outcomes
5. Justification of risks in relation to benefits: Since this study adds use of an EEG cap to existing NCSE protocol without modification of existing method of diagnosis and treatment, risk to patients is minimal and consists of incorrect diagnosis of NCSE and administration of medications that would not otherwise be indicated. However, we believe that verification of EEG findings by a faculty member experienced in EEG interpretation will minimize this risk. Further, misdiagnosis is an existing risk under the current NCSE protocol. If seizure activity is missed on cap electrodes, this would have been missed anyways prior to standard electrode application

H. Data and Safety Monitoring

1. Data and Safety Monitoring Board

- a. Patient charts will only be accessed at the Mayo Clinic by neurology residents and faculty members. This study will involve review of the medical chart only as is required for treatment of the patient in the hospital setting.
- b. All study data will be electronically stored in a password-protected Excel spreadsheet. No PHI will be recorded. Study results will be presented in aggregate form only.
- c. Adverse events will be limited to misdiagnosis of NCSE and administration of anti-seizure medication to a patient with an alternate diagnosis. However, this is an existing risk with current NCSE protocol.
- d. In the event of an unexpected disclosure, the IRB will be notified. The affected patients and their care providers will be informed about the disclosure.

2. Data and Safety Monitoring Plan: [name] will supervise the research and data collection process. All procedures will be recorded as a part of video EEG monitoring. In the unlikely event that unforeseen safety concerns arise, the study will be brought back to the IRB for further review or terminated.

I. Literature Cited

3. Guidelines for epidemiologic studies on epilepsy. Commission on Epidemiology and Prognosis, International League Against Epilepsy. *Epilepsia* 1993; 34:592.

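### A t-test against zero on time to diagnosis says little when the cap is applied first by rule; report the time saved, with its interval, over all consented patients

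*Combined protocol and SAP*

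**What the plan says.** **Hypothesis and endpoint.** The Abstract states that the "time required for diagnosis of NCSE in our institution can be significantly decreased with rapid placement of an EEG cap". Section C gives "Primary outcome measure: time from stat EEG order to diagnosis or exclusion of NCSE". Aim 1 is to "Utilize EEG cap for rapid assessment of seizure activity in 20 patients with suspected NCSE".

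**Order of the recordings.** Section C requires the standard EEG to be ordered before the cap goes on, and says that billing covers "only the subsequent standard EEG protocol which will be followed after the EEG-cap placement". Section G says that "the only deviation from standard of care involves application of EEG cap prior to standard of electrodes". Item 1d of that section adds: "Standard electrode placement will be given priority in the event EEG technician is available before EEG cap is placed". The study runs only when no technician is on site.

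**Analysis.** The statistical methodology is one sentence: "chi-square and Student T-test will be employed", described there as being for categorical variables. It gives no null value, significance level, pairing or minimum useful saving. It does not say how a patient is counted if the technician came first or if the cap gave no decision before the standard EEG.

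**Data items.** The 10- and 20-minute recording times are listed for both devices. The time of diagnosis or exclusion is listed once, without that note.

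**The concern.** A default Student t-test asks whether the mean difference is zero. Here the protocol pushes that difference away from zero before any data are seen. A cap that is placed starts ahead of the standard electrodes, and where the technician would have been ahead, the standard electrodes take precedence. The patients with a cap time are therefore mainly those in whom the cap was quicker.

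Two things follow. A small p-value in those patients may mostly restate the order of application, and it cannot separate a trivial saving from a useful one. An average saving computed in the same patients also overstates what the service would gain over everyone for whom the cap was attempted.

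**Working it through.** **Inputs from the documents.** 20 patients (Aim 1); cap first, technician priority (Sections C and G); Student t-test (Section C). No times, spreads, significance level or power are given, so the plan has no figure of its own to reproduce.

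**Assumed inputs.** Two-sided 5% level. Time from order to start is gamma distributed, identical for resident and technician, with mean 60-90 min and SD 15-45 min. Recording plus reading takes a mean of 25 min, SD 10-20, for both devices.

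**Formulas.** Let S and C be the standard and cap decision times from the stat order, and D = S − C. The clock start cancels in D. Paired test: t = mean(D) / (SD(D)/√20), compared with 2.093 (19 df). The unpaired test uses the pooled SD with 38 df. Only rejections in favour of the cap are counted.

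- *Cap-first patients only:* the earlier of the two start times goes to the cap, the later to the standard EEG.
- *Everyone counted:* saving = S − (first available decision), set to zero if the technician was first or the cap decision came no earlier.

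**Results** (20,000 simulated trials per row; % significant, paired / unpaired, and mean saving):

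| Start mean (SD); reading SD, min | Cap-first only | Cap-first, cap reading 20 min slower (paired) | Everyone counted |
|---|---|---|---|
| 60 (15); 10 | 97.0 / 93.8; 16.8 min | 0.2 | 88.9 / 35.7; 9.3 min |
| 60 (30); 10 | 100 / 99.5; 32.8 min | 41.4 | 92.7 / 46.6; 16.9 min |
| 60 (30); 20 | 95.9 / 92.8; 32.8 min | 27.5 | 88.1 / 36.3; 18.1 min |
| 90 (30); 10 | 100 / 99.6; 33.4 min | 46.7 | 93.4 / 45.1; 17.1 min |
| 90 (45); 15 | 100 / 99.5; 49.2 min | 82.9 | 92.7 / 46.3; 25.3 min |

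If a cap time could be observed in every patient with no ordering rule, the rate would be about 2.5%, the nominal level in one direction.

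**Why the saving roughly doubles.** With identical start-time distributions, each side is first half the time, so the mean of max(S − C, 0) is half the mean of |S − C|. For the second row, 32.8 / 2 = 16.4. Setting negative decision differences to zero lifts this to 16.9. Across the rows the ratio runs from 16.8 / 9.3 = 1.8 to 33.4 / 17.1 = 2.0.

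**Sensitivity to distribution and reading.** With lognormal start times (mean 60 min, log-SD 0.2-0.5), cap-first significance is 90-100% paired and 86-100% unpaired. At log-SD 0.3 and reading SD 5:

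- Cap readings 10, 15 or 20 min slower reduce paired significance to 73%, 18% or 1%.
- If 30%, 50% or 70% of caps give no decision before the standard EEG, it is 99%, 90% or 48% paired, and 74%, 33% or 4% unpaired.

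**Precision of an interval at n = 20.** Half-width = 2.093 × SD(D)/√20. For SD(D) of 15, 30 or 45 min this is 7, 14 or 21 min.

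**The case against.** **Order fixes placement, not diagnosis.** This stands. The endpoint is a decision time. Section G says attendings will hold back from diagnosing NCSE on an uncertain tracing, and Section B treats the cap's accuracy as open. A reader might infer that significance is guaranteed; the slower-reading and unusable-cap results show that it is not.

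**The test against zero is inferred.** This also stands. No section states a null, a level or a rule for claiming benefit, and the word in the Abstract could be meant loosely. A zero null is the default for the named test, and nothing in the plan replaces it.

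**The 93-100% needs technician-first patients to be left out.** Correct, and the documents neither say that they are left out nor that they are kept. Counting everyone does not restore the nominal rate, though. That would need an undistorted cap time in patients where the technician was first, which the priority rule does not supply. What can be observed is the first decision against the standard decision, a difference that is never negative.

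**Avoided waiting is a real gain.** Agreed. The standard EEG is ordered before the cap and, under Aim 3, must not be delayed by it. It would be wrong to read the whole saving as an artefact; when everyone is counted, those minutes are genuine. That argues for estimating them, not for testing whether they differ from zero.

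**The recorded times can show a useful saving.** They can, if logged for each device. The limitation lies in a bare p-value, not in the data.

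**Conclusion.** The point holds in a limited form. Among cap-first patients with similar reading times on both devices, a t-test against zero would favour the cap in about 93-100% of trials even with equally quick starts, and the apparent saving would be roughly twice that over all patients. This rests on assumed times, on a zero null, and on an analysis set that the plan leaves open. It weakens if cap readings are slow or often unusable.

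A reader might go further and use the Abstract's statement that "NCSE becomes more refractory to treatment after one hour of seizure activity" to make the proportion decided within 60 minutes of the order the test of benefit. The documents do not support that. The figure concerns seizure activity, not time from an order, and has no bearing on patients in whom NCSE is excluded. A paired test of that proportion would again be a test against zero under the same ordering. In the equal-speed, cap-first model it declares benefit in about 58-60% of trials in two scenarios and 0-10% in the other three, depending on where 60 minutes falls.

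**What to change.** 1. Make the primary result the within-patient time saved: standard decision time minus first available decision time, both from the stat order. Report a mean or median, chosen in advance, with a 95% confidence interval, in place of a t-test p-value against zero. If many patients have zero saving the median may itself be zero, so give the number of zeros beside it.
2. Log the time of diagnosis or exclusion separately for cap and standard EEG.
3. Include all consented patients. Count technician-first patients, and caps that give no decision before the standard EEG, as zero saving. Say whether the 20 refers to consented patients or to caps placed.
4. State that significance against zero is largely expected from the order of application, and base the conclusion on the size of the saving and its interval. The saving the sponsor would call useful should be written down beforehand.
5. The proportion decided within 60 minutes of the order may be reported descriptively, not as the criterion for benefit.

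The cost is protocol wording, one extra time stamp and a few lines of analysis, with no added procedures. The downside is a less favourable headline than a small p-value, and a fairly wide interval at n = 20.

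### The primary outcome compares cap with standard EEG in the same patient, but the plan lists one unlabelled diagnosis time and does not say what time a patient contributes when the cap reading reaches no decision

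*Combined protocol and SAP*

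**What the plan says.** All references are to the combined protocol and SAP.

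- **Primary outcome (Section C):** "Primary outcome measure: time from stat EEG order to diagnosis or exclusion of NCSE". No device is named.
- **Methods text (Section C):** "We will also record time to confirmation or exclusion of NCSE". No device is named here either.
- **Data list (Section C):** the recording times carry a device label, as in "Time that 20 minutes of EEG have been completed (for both cap & standard-electrodes" and the matching 10-minute line. The next line, "Time of diagnosis or exclusion of NCSE", carries none.
- **Aim 4 (Section A):** "Evaluate endpoints for cap vs. standard electrodes of time from consultation to" a completed EEG (4a) and a decision on NCSE (4b). This states the comparison by device, with the clock starting at consultation.
- **End of Section D:** the authors plan to compare the two methods on the interval from order to interpretation.
- **Secondary outcomes (Section C):** "Concordance between cap & standard-electrode diagnostic assessments", which needs a diagnosis from each device.
- **Risks (Section G):** attendings are expected not to call NCSE when the tracing leaves doubt. Item 1d gives standard electrodes priority if the technician is available before the cap is on.
- **Exclusions (Section C):** the number of excluded patients and the reasons are to be recorded.
- **Statistical methodology (Section C):** chi-square and Student t-test, without saying whether the t-test is paired.

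**The concern.** There is no separate control group. The comparator for the cap's decision time is the decision time from the same patient's standard EEG, so the primary analysis needs two decision times per patient. The data list shows two times for recording but only one for the decision. A data collector working from that list could fill in one field, and a bedside decision time that is not noted when it happens may not be recoverable later.

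Labelling the time does not settle the second gap. A cap recording can be made and read without yielding a decision, and that patient then has no cap decision time. The plan does not say whether the patient is left out, counted at the standard-EEG time, or treated in some other way. A t-test on the available cap times leaves the patient out by default. Those left out are the patients in whom the cap did not help, so the default favours the cap.

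**Working it through.** The plan states no effect size, standard deviation, power or error rate for this outcome, so there is no figure of its own to reproduce. The check compares the texts and then works out what the choice of rule does.

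**1. What has to be recorded.** Aim 4b and Section D require a decision time for each device. The concordance outcome requires a decision from each device, but not its time. The Methods sentence and the data list give one decision time without a label. The intent is clear, but the data field that serves it is not specified.

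**2. Where a cap decision time may be missing.**
- *Cap read, no decision.* The Section G remark on doubtful tracings makes this plausible. The 50% interpretability rule and the third reader in Section C belong to the secondary assessment and are not linked to the primary time.
- *Technician available before the cap is placed.* Such a patient has no cap recording. Aim 1 counts 20 patients in whom the cap is used, so this patient may belong with the recorded exclusions and not among the 20. The plan does not say which.

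**3. Effect of leaving undecided caps out.** Let D be the mean saving (standard minus cap) among patients with a cap decision, and f the share without one. If an undecided cap saves no time, the decision comes from the standard EEG and the difference is 0. That value also relies on Aim 3, "cap to not delay standard of care".

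- Mean saving, decided caps only: D
- Mean saving, all patients: (1-f) × D + f × 0 = (1-f)D
- Ratio: D / [(1-f)D] = 1/(1-f)

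The documents give no value for f, so the range below is assumed. N = 20 is from Aim 1.

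| f (assumed) | Expected undecided, 20f | Chance of at least one, 1-(1-f)^20 | Ratio 1/(1-f) |
|---|---|---|---|
| 5% | 1.0 | 0.64 | 1.053 |
| 25% | 5.0 | 0.997 | 1.333 |

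In minutes, with assumed mean times of 60 (cap) and 120 (standard), D = 120 - 60 = 60. With 1 of 20 undecided, the all-patient saving is 19 × 60 / 20 = 57. With 5 of 20 undecided, it is 15 × 60 / 20 = 45. The decided-only result is 60 in both cases.

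**4. Start point.** Let L be a patient's lag from consultation to order, C the cap time and S the standard time, both from the order. From consultation the difference is (S + L) - (C + L) = S - C. With an assumed L of 20 minutes, 60 and 120 become 80 and 140, and the difference is 60 on either clock. Both start times are on the data list.

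**The case against.** **The comparison is clear enough already.** Aim 4b, Section D and the concordance outcome all point to a comparison by device. The data list is introduced as what the data points include, and it is not exhaustive: it omits the time of cap placement, which the Methods say will be recorded. A reader might infer from the single unlabelled line that the primary contrast cannot be computed at all. The documents do not support that, because a missing label in an incomplete list is weak evidence that only one time will be taken. This objection stands and reduces the label to a clarification, though one best made before data collection.

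**The Section G remark concerns false positives.** It says a positive call is withheld, not that the reading is left open instead of called negative. This also stands. Undecided readings are a plausible inference from the text and not something it states.

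**The size is not known.** A reader might take the 87% technically adequate figure that Section D reports from a cited headset study and infer that 13% of caps here will be undecided. The documents do not support that step. The figure is worded as a share of the EEG and need not mean patients, it comes from another device and setting, and technical inadequacy is not the same as no decision.

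**A decided-caps result is legitimate.** It is, if it is labelled as such and the number undecided is given. The term overstated applies when the result is read as the saving for all patients given a cap. The need to fix the rule in advance remains.

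**The start points differ.** A reader might infer that Aim 4 and the primary outcome would give conflicting comparisons. Step 4 shows that the within-patient difference is the same. Only absolute times, ratios and an unpaired test depend on the start point.

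**Conclusion.** The point holds in a limited form and should be acted on, with medium confidence. The plan intends a within-patient comparison of decision times. It does not label those times by device, and it has no rule for a patient whose cap reading reaches no decision. Dropping such patients would make the result describe only caps that worked, and the direction of the error favours the cap.

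The size depends on an unknown share f. For an assumed 5% to 25%, the mean saving is overstated by 5% to 33%, provided that undecided caps save no time and that the saving is meant for all patients given a cap. If every cap yields a decision, there is no effect. The difference in start points is a minor inconsistency with no effect on the within-patient difference.

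**What to change.** 1. In the data list and the Methods sentence, record the decision time separately for cap and standard electrodes.
2. Define the primary outcome as the within-patient difference, standard minus cap, measured from the stat order. This also settles that the t-test is paired.
3. In the main analysis, give patients with no cap decision their standard-EEG decision time (difference 0). Report the decided-caps-only result and the number undecided beside it.
4. State whether patients whose technician is available before the cap is placed count as recorded exclusions or as patients with no cap decision.
5. As a minor consistency edit, align the start point in Aim 4 with that of the primary outcome.

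The cost is some rewording, plus one extra timestamp and one decided/undecided field for each of 20 patients. The reported saving may be smaller once undecided caps are counted.
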